**2.6. Inclusion and Exclusion Criteria.**

The same inclusion/exclusion criteria will apply to both phases of the study.

**2.6.1. Inclusion Criteria.**

1. SARS-CoV-2 infection confirmed by PCR from a nasopharyngeal swab or other accepted specimen type. (If testing was performed $\geq 5$ days before enrollment, this must be repeated and accept only if positive again). Date of COVID test must be $\leq 5$ days prior to infusion
2. Currently hospitalized adult patient ( $\geq 18$ years of age) requiring medical care for COVID19
3. Peripheral oxygen saturation (SpO2) $\geq 92\%$ on room air
4. Hgb $\geq 7.0$ gm/dl
5. Negative pregnancy test (if applicable)
6. Patient or parent/guardian capable of providing informed consent (may be obtained electronically)
7. Evidence of pulmonary infiltrates on chest imaging. Any chest imaging findings which would be consistent with COVID19 would qualify (Eg: ground glass opacities, multifocal infiltrates etc.)

8.	High risk of requiring mechanical ventilation as defined by at least two of the following :
a.	Age $\geq$ 60 years of age
b.	Age $\geq$ 75 years of age (counts as meeting two criteria)
c.	Hypertension
d.	Chronic cardiovascular disease other than HTN (eg: Coronary artery disease, congestive heart failure or cardiomyopathies).
e.	Diabetes Mellitus
f.	Obesity (BMI $\geq$ 30)
g.	Obesity (BMI $\geq$ 40, counts as meeting two criteria)
h.	Active cancer diagnosis or ongoing (within 3 months) cytotoxic chemo/ radio-therapy for a cancer
i.	Post-hematopoietic stem cell or solid organ transplantation status
j.	Immunodeficiency states including HIV infection on antiretroviral therapy (except those listed as exclusion criteria #1, #7 and #10) as determined by the treating physician (eg: receiving immunosuppressive therapy like rituximab or congenital immunodeficiency syndromes, prior treatment with chemotherapy > 3 months ago but per investigators discretion could have lingering effects on the immune system, eg: chemotherapy regimens for lymphomas, ALL or AML etc.)
k.	Chronic obstructive pulmonary disease (COPD)
l.	Current everyday smoker
m.	Chronic kidney disease (eGFR < 30 mL/min/1.73 m  )
n.	Bronchial asthma (on active treatment prior to admission, eg. Use of rescue inhalers or inhaled corticosteroids or other treatments to prevent/treat attacks).

**2.6.2. Exclusion Criteria.**

1.	Received ATG, Campath or other T cell immunosuppressive monoclonal antibodies in the 28 days prior to screening for enrollment
2.	Requiring mechanical ventilation at time of T cell infusion
3.	Alanine aminotransferase or aspartate aminotransferase > 5 x upper limit of normal
4.	If previously undergone an allogeneic HSCT and have evidence of active acute GVHD $\geq$ grade 2
5.	Uncontrolled relapse of malignancy
6.	Requiring vasopressors
7.	Known history of autoimmune disease except prior thyroiditis
8.	Is not suitable at the discretion of the treating physician
9.	Patients on > 6 mg/day of dexamethasone (IV) per day or equivalent
10.	> grade 1 CRS per ASTCT criteria
11.	Patients should not be enrolled on any other interventional clinical trials for COVID19. Patients may receive routine care for COVID19 per institutional standards (including antivirals such as remdesivir or other FDA-EUA approved products and thromboprophylaxis).

### **2.6.3. Informed Consent and Randomization.**

The informed consent process will begin at recognition of a subject who meets all eligibility criteria and consents to participation after a discussion with the study team (informed consent process). Consent may be obtained by teleconference. Once enrolled, blood will be taken from the subject for baseline immune response assessment and HLA-typing and if a partially HLA-matched VST line is available the subject will either receive treatment (dose escalation phase) or will be randomized (Randomized trial phase) to receive the partially matched VST line (in the treatment arm) or standard of care (in the control arm). If no VST line is identified, the patient will not proceed to treatment or randomization and will be removed from the study, but statistics on the proportion of patients who sign consent but are not treated or randomized will be reported.

Applicable only to the randomized phase, once randomized to the treatment arm, the patient must be infused with VSTs within 48 hours of randomization.

All consented patients will be registered in the online collaborative research environment (Forte's OnCore® eResearch CTMS), a Clinical Research Management System available at BCM Dan L. Duncan Comprehensive Cancer Center.

Enrollment to the dose escalation phase will be staggered. The first patient enrolled on each of the 3 dose levels (DL1, DL2 and DL3) will have to complete the 14-day toxicity monitoring window prior to enrollment of the next patients. Prior to dose escalation, all patients at a particular dose level should have completed the minimum 14-day toxicity monitoring window before enrolling to a higher dose level.

After the dose finding phase, patients will be randomized in a 1:1 ratio to receive SARS-CoVSTs at the MTD level or standard of care. Randomization will be performed in OnCore and use the permuted block method with a block size of 4 (2 in the treatment arm and 2 in the control arm). The purpose for a permuted block method is to ensure fairly random assignment during specific periods of surge with COVID19.

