### **2.2. Primary Objective for randomized pilot trial phase.**

To study the anti-COVID19 efficacy of administering banked partially HLA-matched SARS-CoVSTs to hospitalized COVID19 patients.

**2.2.1 Primary end point:** Response, defined as a  $\geq 2$  improvement in the WHO Ordinal Scale or discharge from hospital, by day 7 post-randomization. The scale is shown in [Appendix III](#). Response data will be summarized by the proportion of patients in the treatment arm vs the control arm who have a response.

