#### **2.7. Standard of care arm (only for the randomized phase of this study).**

Patients randomized to the standard of care arm will continue to receive treatments for COVID19 as determined by institutional protocols. They will not receive a placebo.

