### **3.3. Assessments during the study.**

The timing of events as per the schedule in Table 1 above is based on the date of receiving VST infusion (dose escalation phase) or from randomization (randomized phase). Additional follow up assessments may be done based on clinical and laboratory responses.

All assessments are considered standard-of-care unless identified.

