#### **4.5. Sample Size Determination and Design Characteristics**

A maximum of 18 DLT evaluable patients will be accrued to the dose finding phase of the study. Based on our previous studies and experiences, we do not anticipate seeing any VST-related AE at any dose level and we expect to enroll 12 for the phase.

In the randomized pilot trial phase, a total of 40 patients will be enrolled and randomized (20 in the treatment arm and 20 in the standard of care arm). The safety endpoint in this phase is tAE. The study is designed to monitor toxicity due to SARS-CoVSTs closely so the trial can halt accrual early if its toxicity rate is excessive. For this purpose, a tAE rate of 25% is considered excessive, while a rate below 25% is considered acceptable. Based on our current experience with VST therapy, we anticipate the actual tAE rate to be much lower around 5%. With 20 patients in the treatment arm, if the observed tAE rate is 5%, the corresponding 95% confidence interval will be 0.1%-24.9% which excludes 25%, and the chance of observing more than 3 tAEs in the treatment arm is only about 1.6%. The efficacy endpoint in this phase is clinical response, defined as improvement in at least 2 points in the WHO Ordinal Scale or discharge from hospital by day 7 post randomization. Patients' outcome will be dichotomized as 'having a response' or 'not having a response'. Patients who died before day 7 will be deemed as 'not having a response'. Based on current publications of novel COVID-19, we expect 90% patients in the treatment arm and 50% patients in the control arm will have a response by day 7. A sample size of 40 will provide 83% power to detect the 40% increase in response rate for the SARS-CoVSTs treatment compared to the standard of care treatment, with a Fisher's exact test at a 5% one-sided significance level.

We anticipate about one third subjects who are considered for study participation will not meet all inclusion criteria, thus we will consent 87 subjects to have 58 eligible patients (18 in dose finding phase and 40 in the randomized pilot trial phase).

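### Response is counted from randomization but VST infusion may follow up to 48 hours later, so up to 2 of the 7 days in the VST arm can be control care, an avoidable dilution of the contrast

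*Protocol*

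**What the plan says.** Protocol section 2.2.1 defines the primary endpoint as a gain of two or more points, "improvement in the WHO Ordinal Scale or discharge from hospital, by day 7 post-randomization". Section 3.3 says that the timing of the assessments in Table 1 "is based on the date of receiving VST infusion (dose escalation phase) or from randomization (randomized phase"), so day 0 of the randomized phase is randomization in both arms.

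Section 2.6.3 requires that a partially matched line be available before a patient is randomized. It then allows an interval before treatment: "the patient must be infused with VSTs within 48 hours of randomization". A footnote to Table 1 and the day-of-randomization list in section 3.3 repeat the limit. No section gives an expected interval or requires an infusion time to be arranged before randomization.

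The comparator is in section 2.7: "Patients randomized to the standard of care arm will continue to receive treatments for COVID19 as determined by institutional protocols", without placebo.

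Section 4.5 defines response on the same clock, "defined as improvement in at least 2 points in the WHO Ordinal Scale or discharge from hospital by day 7 post randomization", and then gives the planning rates: "we expect 90% patients in the treatment arm and 50% patients in the control arm will have a response by day 7". With "20 in the treatment arm and 20 in the standard of care arm", it states: "A sample size of 40 will provide 83% power to detect the 40% increase in response rate", using a one-sided 5% Fisher's exact test. Section 4.6 analyses efficacy by intent to treat.

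**The concern.** Until the infusion, a patient in the VST arm receives what a control patient receives. The window is only 7 days, so a 2-day wait takes up a sizeable part of it, and the product has as few as 5 days in which to act before response is read. Any real effect would then show as a smaller difference between arms. With 20 patients per arm and power only slightly above 80%, there is little room for that, and a negative result would be harder to attribute to the product rather than to the wait.

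The wait also looks largely avoidable. HLA typing and line identification come before randomization (section 2.6.3), and the lines are already banked, tested and cryopreserved (sections 1.5 and 2.6.4). What remains between randomization and infusion appears to be mainly scheduling.

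**Working it through.** **1. Share of the window.** 48 hours is 2 days, and 2/7 = 28.6%. The shortest post-infusion time before the day-7 reading is 7 − 2 = 5 days for a patient infused at the limit.

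**2. The plan's own power.** Inputs from section 4.5: 20 per arm, 90% against 50%, one-sided Fisher's exact test at 5%. Summing the binomial probabilities of all 20-against-20 outcomes with one-sided p ≤ 0.05 gives 83.7%. The stated 83% reproduces.

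**3. Sensitivity to the VST rate.** Same test, control fixed at 50%:

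| VST response by day 7 | Power |
|---|---|
| 90% | 83.7% |
| 89% | 81.1% |
| 88% | 78.4% |
| 85% | 69.3% |
| 80% | 53.1% |

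Power is below 80% at 88%, only 2 points under the planning rate.

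**4. What a wait would do if the 90% ignores it.** The protocol does not say this; it is an assumption. A second assumption is a constant daily response rate in each arm that reproduces the planning figures, with the VST rate starting at infusion:

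- control rate = −ln(0.5)/7 = 0.099 per day
- VST rate = −ln(0.1)/7 = 0.329 per day
- VST-arm response with a wait of d days = 1 − exp(−[0.099·d + 0.329·(7 − d)])

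| Wait d, all VST patients | Response by day 7 | Power against 50% |
|---|---|---|
| 0 | 90.0% | 83.7% |
| 0.5 day | 88.8% | 80.5% |
| 1 day | 87.4% | 76.7% |
| 2 days | 84.2% | 66.7% |

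The result depends on the model. If the 40-point difference instead shrinks in proportion to the days lost, response is 50% + 40%·(7 − d)/7. That gives 84.3% and power of 67% at 1 day, and 78.6% and power of 48% at 2 days.

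**5. If the 90% already includes the wait.** The response rate by day 7 after randomization is then 90% by definition, and power stays at 83.7%.

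**6. Does keeping a patient in hospital for the infusion bias the endpoint?** Response is cumulative by day 7. Suppose VSTs have no effect and a patient is held until infusion on day 2. Discharge then occurs at the later of day 2 and the day the patient is ready to leave. The chance that this falls by day 7 equals the chance of being ready by day 7, which is 50%, the same as control. In this model the bias is zero.

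**The case against.** The strongest counter-argument is that the design is the ordinary one. Counting from randomization under intent to treat keeps the arms comparable. Starting the clock at infusion in the VST arm alone would give that arm a longer window. A VST patient who leaves before infusion is counted in the assigned arm, as intent to treat requires. All of this stands, and the point does not ask for the clock to move.

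A reader might infer that the 83% power is not delivered. The documents do not support this: section 4.5 states the endpoint by day 7 after randomization and then gives 90% and 50% by day 7, so the rates can be read as already containing the wait.

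A reader might also infer a built-in bias against VSTs, because a patient held for infusion cannot go home while a matching control can. That does not follow either. The held patient can be discharged after infusion and still count by day 7 (step 6). Section 2.6.5.2 sets minimum post-infusion observations only up to 60 minutes, and no section says that patients are to be kept in hospital for the infusion.

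Finally, 48 hours is a ceiling, and an off-the-shelf product suggests that the usual wait is shorter. That is fair, and the 2-day row in step 4 is an extreme. But the protocol gives no expected wait, and requiring an available line is not the same as having an infusion time arranged.

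**Conclusion.** The point holds as an avoidable dilution of the treatment contrast, not as an error in the power calculation. Up to 2 of the 7 days in the VST arm can be control care; this follows directly from the text. The 83% is arithmetically right on the plan's inputs.

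Power would be lower only if the 90% assumes treatment from day 0. In that case, under constant daily rates, it would be about 81%, 77% or 67% if all VST patients waited 0.5, 1 or 2 days. Those figures rest on an interpretation that the protocol neither states nor excludes, on a common wait that it does not give, and on a response model chosen for illustration. No directional bias from waiting in hospital is shown. This is a low-cost improvement rather than a flaw that invalidates the comparison.

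**What to change.** In sections 2.6.3 and 4.3, state that a patient is randomized only once the matched line has been released and an infusion time has been confirmed, so that randomization and infusion are planned for the same day. Leave the intent-to-treat clock from randomization and the existing 48-hour limit unchanged. One sentence in section 4.5 saying whether the 90% allows for the interval before infusion would also settle how the 83% is to be read.

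The cost is protocol wording and the scheduling of the randomization step. Randomization may be slightly later in both arms, and a few patients may improve, worsen or leave before it. No extra patients or procedures are needed.

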### 4.3 Randomized Pilot Trial Phase

After the MTD is determined, the study will continue to the randomized pilot trial phase. Consented and eligible patients in this phase will be randomized in a 1:1 ratio to receive either SARS-CoVSTs on the MTD level or standard of care. Randomization will employ the permuted blocks method with a block size of 4 (2 in the treatment arm and 2 in the control arm). No stratification will be used in randomization.

In the randomized pilot trial phase, we will continuously monitor the safety of SARS-CoVST infusions in the treatment arm so that the accrual can be halted early if there is an unexpectedly high rate of treatment-related adverse events. Treatment-related adverse events (tAE) are defined in Section 3.1. Every patient who is randomized to the treatment arm and infused with SARS-CoVSTs will be evaluated for tAE and all patients who have tAEs will be followed until toxicities resolve. A tAE rate of greater than or equal to 25% is considered excessive. The occurrence of tAEs will be monitored using a stopping guideline based on a Pocock-type boundary method [24]. The following sequential stopping boundaries will be used:

Number of Patients	1-2	3	4-5	6-7	8-9	10-12	13-15	16-17	18-20
Number of tAEs <	-	3	4	5	6	7	8	9	10

The accrual will be halted if the number of tAEs is equal to or exceeds the boundary in the above table. Under this sequential stopping rule, the probability of early stopping is 5% if the true tAE rate is 25%, and the probability of early stopping will be high at 67.5% if the true tAE rate is 50%.

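### A fixed, published block size of 4 in an open-label, unstratified trial lets anyone who tracks allocations know one third of assignments in advance

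*Protocol*

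**What the plan says.** Protocol section 2.6.3 states that, after dose finding, "patients will be randomized in a 1:1 ratio to receive SARS-CoVSTs at the MTD level or standard of care". It places randomization in OnCore and says that it will "use the permuted block method with a block size of 4 (2 in the treatment arm and 2 in the control arm"). Section 4.3 repeats the block size and adds: "No stratification will be used in randomization". The reason given in 2.6.3 for blocking is to keep assignment balanced during COVID-19 surges.

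Allocation is open. Section 2.7 says of the control patients: "They will not receive a placebo". On the other arm, section 2.6.3 requires that "once randomized to the treatment arm, the patient must be infused with VSTs within 48 hours of randomization".

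Eligibility is partly a matter of judgement. Exclusion criterion 8 in section 2.6.2 reads: "Is not suitable at the discretion of the treating physician". The primary endpoint (section 2.2.1) is an improvement of at least 2 points on the WHO ordinal scale, or hospital discharge, by day 7 after randomization. Section 4.6 analyses efficacy by intention to treat.

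The protocol nowhere says that block sizes vary or are withheld from those who enrol patients.

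**The concern.** Holding the list centrally conceals the next assignment only if it cannot be worked out from what is already known. Here three facts combine: the block size is printed, there is only one sequence to follow, and each past assignment can be seen. Once two patients in a block have gone to the same arm, the next two are known. The fourth patient in every block is always known.

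Foreknowledge matters where someone can act on it before randomization. The discretionary exclusion gives that room: a borderline patient can be put forward, held back or judged unsuitable in light of the arm that comes next. The endpoint depends on how ill the patient is at entry, and its discharge component is decided by clinicians who know the arm. Intention-to-treat analysis preserves the groups as randomized. It does not correct for who was let into each group.

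**Working it through.** **The plan's own figure.** Section 4.5 gives 83% power for 20 against 20, response 90% against 50%, Fisher's exact test at one-sided 5%. Summing over all 21 × 21 outcomes gives 83.7%. The power statement is sound and is not at issue. The protocol gives no figure for predictability, so that is derived here.

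**Inputs.** Block size 4, split 2:2 (2.6.3, 4.3); one sequence (4.3); 40 patients, hence 10 blocks (4.5); past assignments visible (2.6.3, 2.7).

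**Certain assignments.** Write T for treatment and C for control. A block has six equally likely orders.
- TTCC and CCTT: the last two assignments are certain.
- TCTC, TCCT, CTTC and CTCT: only the last is certain.

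Expected number per block = (2 × 2 + 4 × 1)/6 = 4/3, and (4/3)/4 = 33.3%. Over ten blocks this is 13.3 of 40, with SD √(10 × 1/3 × 2/3) = 1.5, minimum 10 and maximum 20.

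**Best guess.** Always guess the arm with more places left. The chance of being right by position is 1/2, 2/3, 2/3 and 1. The mean is (17/6)/4 = 17/24 = 70.8%, against 50% by chance.

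**Possible bias (hypothetical).** Assume no true effect and a 50% response rate. Assume also that steering happens only when the next assignment is certain: a patient known to be going to treatment responds with probability 50% + d, and one known to be going to control with 50% − d. By symmetry one third of each arm is affected, so the difference shifts by d/3 + d/3 = 2d/3. The false-positive rate of the one-sided 5% Fisher test was computed exactly by combining ten blocks; 10,000 simulated trials per row are given beside it.

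| Assumed d (points) | Bias 2d/3 (points) | False-positive rate, exact | Simulated |
|---|---|---|---|
| 0 | 0 | 2.1% | 2.4% |
| 10 | 6.7 | 5.3% | 5.6% |
| 20 | 13.3 | 11.4% | 11.8% |

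**Effect of other block schemes.** For mixed sizes, 40-patient sequences were simulated with each size equally likely. The observer is assumed to know the set of sizes and all past assignments, but not the order of the sizes.

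| Scheme | Certain | Best guess right |
|---|---|---|
| Fixed 4 (plan) | 33.3% | 70.8% |
| Fixed 6 | 25.0% | 68.3% |
| Fixed 8 | 20.0% | 66.6% |
| Mixed 2, 4, 6 | 3.8% | 70.0% |
| Mixed 4, 6 | 5.6% | 68.9% |
| Mixed 4, 6, 8 | 2.2% | 67.8% |

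Varying the size removes most of the certainty, which a longer fixed block does not. It does little to best-guess accuracy. Including size 2 nearly cancels even that gain, because a block of 2 is guessed correctly 75% of the time.

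**The case against.** The strongest reply is that this is a 40-patient pilot, that fixed small blocks contradict nothing in the protocol, and that safeguards exist. The list is in OnCore. HLA typing and the search for a matched line come between consent and randomization, so at consent the team cannot be sure whether, or in which position, a patient will be randomized. The share of consented patients who are not randomized is to be reported. The discretionary exclusion belongs to the treating physician, who is not shown to be following allocations, and the same item is already on the eligibility checklist, which a physician signs and dates. All of this stands. It makes steering harder, but it does not prevent deduction from a known block size and a visible history.

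A reader might infer a stronger case on four counts, and the protocol supports none of them.
- **That steering will happen.** The text shows an opportunity only.
- **That a bias of about 8 points is to be expected.** That value comes from 2 × 10 × (2 × 0.708 − 1) = 8.3. It assumes action on every guess, including the coin toss at the start of each block, and a 10-point shift for which the protocol gives no basis.
- **That this is a single-hospital trial.** Section 3.3 names one hospital for late visits and for the investigators, but the protocol never says that the randomized phase has one site. Several sites sharing the sequence would make tracking harder.
- **That the endpoint is discharge alone.** It is a 2-point improvement or discharge.

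**Conclusion.** The concern holds as a weakness of design that is cheap to mend, not as an error. An expected one third of assignments (13.3 of 40, never fewer than 10 in ten complete blocks) can be known beforehand. This is exact arithmetic, on two conditions: the observer knows the block size, which the protocol prints, and has followed the earlier allocations, which are open.

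The consequence for the primary comparison is conditional. With no steering the bias is zero. With steering confined to certain assignments it is 2d/3, where d is an assumption. On that model a 10-point shift takes the false-positive rate only just past the nominal 5%, and a 20-point shift roughly doubles the nominal rate. The power calculation is unaffected.

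**What to change.** In sections 2.6.3 and 4.3, replace the fixed block size by permuted blocks of randomly varying size, for example 4, 6 and 8, and avoid size 2. Keep the sizes in a restricted randomization file that those who enrol patients cannot see, and do not state them in the protocol. The OnCore list must be regenerated as well as the text changed.

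If the set of sizes became known anyway, certain assignments would still fall from 33% to about 2%. Best-guess accuracy would fall only from about 71% to 68%, so the gain is mainly the removal of certainty. Balance during surges is kept, because the blocks remain short.

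Cost: two edited passages, a new list, and a temporary or final difference of up to 4 patients between arms (half of a block of 8). The total of 40 need not change. In the worst case, 22 against 18, recalculated power is about 82%. The treatment arm could then pass 20, where the stopping table in section 4.3 ends, so that table should be extended to 22.
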